**C7b. Measures of Relative Reinforcement and Dependence:** Relative reinforcement will primarily be assessed using a lab-based preference assessment, a well-validated measure of reinforcement value. First, participants will sample their usual brand cigarette to standardize time since last cigarette. Then participants will sample their assigned e-cigarette and e-liquid. Immediately after sampling each product, participants will complete questionnaires about that product, including a modified version of the mCEQ, a perceived health risk measure, and a purchase task. Then, participants will complete the preference assessment in which over a period of 30-minutes and 10 trials (three-minute inter-trial interval), participants choose between taking two puffs of the e-cigarette, two puffs of their usual (own) brand cigarette, or abstaining from both. This task measures the impact of concentration and power on changes in the relatively reinforcement value of smoking compared to using the e-cigarette. The primary outcome is the number of choices to smoke the usual brand cigarette, but secondary outcomes include the number of choices to use the e-cigarette and to abstain. We considered utilizing a cigarette other than the participant's usual brand to control for novelty, but changes in relative reinforcement value of the participants' usual brand cigarette are most relevant from a public health perspective. Our lab space includes ventilated smoking rooms equipped with cameras and intercom, which allow us to guide participants through the task from a separate area. A secondary measure of reinforcement value will be the purchase tasks—hypothetical tasks in which participants estimate the intensity with which they would use cigarettes and e-cigarettes at a variety of prices. An individual's sensitivity to the cost of a tobacco product is considered to be an estimate of that product's reinforcement value. Dependence will be assessed at in-person visits using established measures of cigarette and e-cigarette dependence (Fagerstrom Test for Nicotine Dependence, Wisconsin Inventory of Smoking Dependence Motives, Penn State E-cigarette/Cigarette Dependence Scale). [name] is utilizing both the preference task and the demand measures in her ongoing pilot trial focused on PG/VG ratio in e-liquids.

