Participants who are eligible will then provide a urine sample for cotinine analysis and complete additional baseline questionnaires including measures of nicotine dependence. Participants will be randomized to one of four groups as described above and will have the opportunity to sample their usual brand cigarette and their assigned e-cigarette and e-liquid for the first time. After sampling each product, participants will complete additional questionnaires and complete the preference assessment where they choose between their cigarette and assigned e-cigarette. At the end of Visit 1, participants will receive a one week supply of e-liquid to take home with their assigned e-cigarette, will be enrolled in the daily electronic diary system, and will be provided with instructions for completing diaries.

Participants will return to the lab for three additional weekly visits, and will receive a new supply of e-liquid for each week. At each visit, we will assess tobacco use during the prior week, participants will provide an expired breath carbon monoxide sample, adverse events will be assessed, and participants will complete questionnaires about their assigned e-cigarette and e-liquid. At the fourth and final weekly visit, participants will complete the sampling and preference assessment again, providing another urine sample for cotinine testing, and return any unused study product.

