## Statistical Analysis Plan

Power analysis was completed for the primary outcome of percentage reduction in average cigarettes per day smoked in the last week of sampling, and based on data from [name] previous e-cigarette sampling trial during which participants received a low power (1st Gen) device with one of two nicotine concentrations (low or high) (84). We hypothesize that the impact of nicotine concentration on CPD reduction would be similar here for the low power groups and that the effect would reversed, but of similar size, in the high-power groups. In this case, a sample size of 40 participants / group will provide 80% power to detect an interaction among the two factors with a 0.050 significance level, assuming that the common standard deviation is 38% reduction in CPD, as was the case in [name] trial (84). However, we inflate this sample size by 10%, accounting for attrition over time, and thus aim to **recruit 45 participants randomized per group (total N=180)**.

For aims 1 and 2, we will assess the impact of concentration and power on each outcome across time using a generalized estimating equation that includes concentration, power, sampling week (time), and their interactions. Hypothesis 1 will focus on percentage reduction in CPD, Hypothesis 2 will focus on e-cigarette uptake (puffs per day), and Hypothesis 3 will focus on complementary measures of preference/demand, all of which are captured at Visit 4. Outcomes that are skewed (e.g., demand parameters, urinary cotinine) will be log transformed. It is possible that reductions in CPD will be bimodal in the last week of sampling, reflecting a subset of participants who may quit smoking during the trial. In this case, we would conduct a Chi-square test on the proportion of participants who reduce their smoking by at least 50%. Exploratory analyses on age will be conducted by adding age to the model. As described in the Career Development Plan, [name] (co-mentor) will be meeting with [name] monthly for training in these analyses, and will also be available to assist with any unexpected issues. Gender will be examined separately as a direct or moderating influence on all outcomes.

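### The Hypothesis 3 model names no pre-exposure covariate, although the Visit 1 cigarette purchase task could serve as one: precision is lost, but no bias arises

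*Combined protocol and SAP*

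**What the plan says.** For Aims 1 and 2 the SAP (and C8, in the same terms) specifies "a generalized estimating equation that includes concentration, power, sampling week (time), and their interactions". It adds that "Hypothesis 3 will focus on complementary measures of preference/demand, all of which are captured at Visit 4". No Visit 1 value is named as a covariate. Age is exploratory, gender is examined separately, and C1 admits flavor only if it proves necessary.

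C7b sets the order of the laboratory session. The opening step concerns the participant's own brand: "First, participants will sample their usual brand cigarette to standardize time since last cigarette". The study product is the second step, and C7b puts it this way: "Then participants will sample their assigned e-cigarette and e-liquid". As for when the questionnaires are given, each set is tied to its own product: "Immediately after sampling each product, participants will complete questionnaires about that product". The list of those questionnaires includes "a perceived health risk measure, and a purchase task". The preference assessment comes last. Table 1 schedules purchase tasks at Visits 1, 4 and 5, and the preference assessment at Visits 1 and 4.

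Section 1.2 (Study Procedures) puts randomization before this session: "Participants will be randomized to one of four groups as described above and will have the opportunity to sample their usual brand cigarette". It is the occasion on which participants "sample their usual brand cigarette and their assigned e-cigarette and e-liquid for the first time". C5a blinds both participants and staff to concentration and power.

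**The concern.** Smokers differ in their demand for cigarettes before they touch a study product. With no pre-exposure measure in the model, those differences stay in the residual variance of the Visit 4 outcomes. C8 itself warns that an interaction is estimated with four times the variance of a main effect, and Hypothesis 3 is an interaction hypothesis. The trial already collects a measure that could remove part of this variance.

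Which Visit 1 measure may be used matters. The preference assessment and the e-cigarette purchase task both follow first use of the assigned product, so they may already carry part of the effect under study. The cigarette purchase task does not. The SAP does not draw this distinction.

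**Working it through.** **1. Order of events at Visit 1.** Combining section 1.2 with C7b gives: randomization (blinded); usual-brand cigarette; cigarette questionnaires including the cigarette purchase task; first use of the assigned e-cigarette; e-cigarette questionnaires including its purchase task; preference assessment. The cigarette purchase task is therefore after randomization but before exposure.

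**2. The plan's own figures.** These concern percentage reduction in cigarettes per day (CPD), not Hypothesis 3.
- Attrition: 40/(1 − 0.10) = 44.4, rounded up to 45 per group, and 4 × 45 = 180. This reproduces.
- Power: the contrast has SE = SD × √(4/n) = 38 × √(4/40) = 12.02. The text gives no effect size, so the 80% can only be solved backwards (two-sided 0.05 assumed): (1.960 + 0.842) × 12.02 ≈ 33.7 points, or opposite simple effects of about 16.8 points each.
- No power is stated for Hypothesis 3.

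**3. Precision for cigarette demand.** Let σ² be the within-cell variance of the (log) demand parameter, n the number per cell, and r the within-cell correlation between Visit 1 and Visit 4. The documents do not give r; 0.2 to 0.8 is an assumed range. Variance of the interaction contrast:
- Visit 4 only: 4σ²/n
- Visit 4 adjusted for Visit 1: 4σ²(1 − r²)/n
- Change from Visit 1, equal variances assumed: 4 × 2σ²(1 − r)/n

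Against Visit 4 only, the SE falls by 1 − √(1 − r²), and 40 completers act like 40/(1 − r²). Against the change contrast, the variance ratio is (1 − r²)/[2(1 − r)] = (1 + r)/2, so the SE falls by 1 − √[(1 + r)/2].

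| r | 1 − r² | SE cut vs Visit 4 only | 40 per cell act like | (1 + r)/2 | SE cut vs change |
|---|---|---|---|---|---|
| 0.2 | 0.96 | 2% | 42 | 0.60 | 23% |
| 0.4 | 0.84 | 8% | 48 | 0.70 | 16% |
| 0.6 | 0.64 | 20% | 63 | 0.80 | 11% |
| 0.8 | 0.36 | 40% | 111 | 0.90 | 5% |

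The percentages do not depend on n. As an illustration, an effect with 80% power in the Visit 4-only analysis at 40 per cell would have 81.6%, 86.4%, 93.8% or 99.7% after adjustment.

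**4. Check on bias.** A simulation used 40 per cell, 1,000 replicates per setting, r of 0.3, 0.5 and 0.7, and an effect sized for 80% unadjusted power.
- Adjusting for a pre-exposure covariate left the mean interaction estimate at 0.98 to 1.02 of its true value, with power of about 82% to 98%.
- Adjusting for a Visit 1 measure assumed to carry half of the effect already shrank the estimate to about 85%, 76% and 66% of its true value.

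**The case against.** **Visit 1 may already be in the model.** The SAP assesses each outcome over time, C7b describes the preference task as measuring changes, and saying when a measure is captured does not say that only that visit is analysed. This stands as an ambiguity, so a reader should not infer that Visit 1 demand is certainly discarded. It changes the size of the gain (last column of the table) but does not remove it. For choices to smoke, that reading would make a post-exposure value the baseline.

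**It is only efficiency, in a trial sized for CPD.** This stands. A reader might infer that the unadjusted analysis is biased, or that the missing power statement for Hypothesis 3 is a defect that this covariate cures. The documents support neither inference: randomization protects the Visit 4 comparison, and the sample size was set on another outcome.

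**The figures belong to the secondary measure.** This also stands. C7b makes choices to smoke the primary outcome of the preference task and purchase tasks secondary, and the Aim 2 hypothesis is worded in choices. The documents give no basis for a figure for choices. Nor do they show that cigarette demand predicts choices better than dependence or cotinine, both collected before randomization.

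**The correlation could be low.** Products that may change demand are used between the two visits. Under C5e, Visit 4 questionnaires may be completed remotely beforehand, away from the standardized session. Hence the range starts at 0.2.

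**Conclusion.** The point holds as a missed gain in precision. The specified Hypothesis 3 model names no pre-exposure covariate, and the stated session order makes the Visit 1 cigarette purchase task a usable one. Its validity rests on that order and on blinding; it is not a pre-randomization measure.

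For cigarette demand, the standard error of the interaction would fall by about 2% to 40% against a Visit 4-only analysis, or by about 23% to 5% against a change contrast, as r goes from 0.2 to 0.8. Both ranges rest on an assumed r and a linear model, and the second also on equal variances. It would be tempting to quote the 40% alone, but that needs r = 0.8 and the Visit 4-only reading; at the same r the other reading gives 5%. For choices to smoke the gain is unquantified and probably smaller, because the covariate is a different measure from the outcome.

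**What to change.** Amend the SAP as follows:
- In the Visit 4 model for each cigarette demand parameter, add the same parameter from the Visit 1 cigarette purchase task, on the same (log) scale, as a main-effect covariate.
- In the Visit 4 model for number of choices to smoke, add one prespecified, named Visit 1 cigarette demand parameter as a main-effect covariate. The outcome is a count from 0 to 10, so the covariate's scale should be stated in its own right.
- State that the Visit 1 preference assessment and the Visit 1 e-cigarette purchase task are not used as baseline values, because they follow first use of the assigned product.

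The cost is SAP wording and one degree of freedom per model: with 4 × 40 = 160 completers and four cell means, residual degrees of freedom go from 156 to 155. No new data, visit or procedure is needed.

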Reinforcement value is the perceived magnitude of a reward. For e-cigarettes, this value is likely a function of both nicotine delivery and sensorimotor cues. Nicotine is the primary pharmacological reinforcer for tobacco use . Nicotine delivery for e-cigarettes is impacted by at least two product characteristics. First, e-cigarettes contain liquid that can be purchased with a wide range of nicotine concentrations. Second, devices vary in how much power is delivered to the heating element. These two characteristics, nicotine concentration and device power, work together to impact the nicotine delivery of the aerosol that is delivered to the user. Survey evidence suggests a negative correlation between the power of a device and the chosen nicotine concentration , likely because users modify their choice of concentration and power such that optimal levels of nicotine are delivered. Aside from nicotine delivery, both the nicotine concentration and the power of the device are important determinants of the sensorimotor cues associated with e-cigarette use, such as the “throat hit” a smoker feels when taking a puff, and the temperature and volume of the delivered aerosol. Despite the importance of these characteristics, no study has experimentally investigated the interaction between these two characteristics on reinforcement value and tobacco use. ***The purpose of this application is to use both lab-based and naturalistic methods to understand how nicotine concentration and device power interact to impact relative reinforcement value and tobacco use patterns.***

Within a 2x2 between-subjects design that manipulates nicotine concentration (3 vs. 12 mg/ml) and device power (20W vs. 40W), daily smokers with limited e-cigarette experience (n=180) will receive e-cigarettes to use ad libitum over a three-week period. Methods include both naturalistic/ecological assessments (daily diaries, an e-cigarette device that captures topography) and experimental sessions to examine reinforcement (preference and purchase tasks). Biomarkers will corroborate self-reported indices of use. Because the public health impact of e-cigarette use is ultimately dependent on changes in cigarette smoking behavior, our primary focus is on changes in smoking and the reinforcement value of cigarettes. We do however test for differences in uptake and reinforcement value of e-cigarettes.

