**Specific Aim 1:** To understand the impact of nicotine concentration and device power on cigarette smoking (cigarettes smoked per day; CPD) and smoke exposure (expired breath carbon monoxide; CO). Hyp1: There will be an interaction such that a higher (vs. lower) nicotine concentration will produce greater reductions in CPD and CO when device power is low, and a lower nicotine concentration will produce greater reductions in CPD and CO when device power is high. Hyp2: Parallel analyses will test the main and interactive effects of nicotine concentration and device power on e-cigarette use (hypothesizing more puffs per day).

**Specific Aim 2:** To understand the impact of nicotine concentration and device power on relative reinforcement value (choices to smoke versus use an e-cigarette in a lab-based preference task, demand for each product on a hypothetical purchase task). Hyp3: There will be a similar interaction such that a higher nicotine concentration will result in fewer choices to smoke a low power device, and a lower nicotine concentration will result in fewer choices to smoke in a high-power device.

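### Does the missing rule for zero demand before log transformation call for a change to the plan?

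*Combined protocol and SAP*

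**What the plan says.** The Statistical Analysis Plan, like section C8 of the protocol, sets one rule for skewed outcomes: "Outcomes that are skewed (e.g., demand parameters, urinary cotinine) will be log transformed". It gives no added constant, two-part or log-link model, exclusion rule or curve-fitting criterion, and it does not list the demand parameters.

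The data come from hypothetical purchase tasks. In section C7b, "participants estimate the intensity with which they would use cigarettes and e-cigarettes at a variety of prices". The same section treats an individual's "sensitivity to the cost of a tobacco product is considered to be an estimate of that product", meaning of its reinforcement value. It also sets the rank of the measure: "A secondary measure of reinforcement value will be the purchase tasks". The primary measure there is the number of choices to smoke in the preference task.

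The Statistical Analysis Plan allows that reductions in cigarettes per day may be bimodal, "reflecting a subset of participants who may quit smoking during the trial". For that case it has a fallback for cigarettes per day: "we would conduct a Chi-square test on the proportion of participants who reduce their smoking by at least 50" per cent. It gives demand no such fallback.

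**The concern.** Zero is an available answer on a purchase task, and log(0) is undefined. A participant who has stopped smoking may report no cigarette demand, and one who has given up the device may report no e-cigarette demand. Sections C1 and C5a let participants leave the e-cigarette unused. The paragraph that provides for quitters on cigarettes per day is silent about them on demand.

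Dropping the zeros would select on a post-randomization response and remove the strongest responders. If Hypothesis 1 is right, these would tend to sit in the two cells expected to do best, so the overall demand interaction would shrink. Adding a constant keeps everyone, but the estimate then depends on the constant and the unit. Someone who would buy nothing at any price has no estimable cost sensitivity, and no constant supplies one.

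Aim 2 names "demand for each product on a hypothetical purchase task" as an outcome, and the Specific Aims state that "our primary focus is on changes in smoking and the reinforcement value of cigarettes". A choice left until the data are seen could therefore affect a result that readers will care about.

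**Working it through.** **No figure to reproduce.** The power calculation concerns percentage reduction in cigarettes per day, so nothing stated in the documents depends on how zeros in demand are handled.

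**How likely are zeros?**
- The Statistical Analysis Plan says only that some participants may quit.
- Abandonment of e-cigarettes appears in the Abstract, the Specific Aims and section A1 as a pattern among smokers in general. It is not a prediction for this sample, which section C3 restricts to people rating their interest in e-cigarettes above 5 on a 0 to 10 scale.
- By section C7b, each purchase task follows directly after the participant samples that product. Section 1.2 (Study Procedures) repeats the sampling at the last weekly visit. A quitter who declines the cigarette may be a missing response and not a zero.

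Zeros are therefore possible, but at an unknown rate.

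**Assumed inputs (none is in the documents except 45 per cell).** Visit 4 cigarette demand has median 12 per day and log SD 0.6 among those with any demand. Amount is 15% lower (a = 0.85) in the two cells expected to do better. Zeros occur with probability pB in those two cells and pW in the other two.

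The interaction ratio multiplies two better-to-worse comparisons:
- overall demand: [a(1 − pB)/(1 − pW)]²
- zeros dropped: a² = 0.85² = 0.7225

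For 15% and 5%: (0.85 × 0.85/0.95)² = 0.578. For 3% and 1%: (0.85 × 0.97/0.99)² = 0.694. Expected zeros are 90 × pB + 90 × pW.

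Ratios are below, with the percentage of simulated trials rejecting at two-sided 5% in brackets where shown:

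| Zeros pB / pW | Expected zeros of 180 | Overall demand | Zeros dropped | log(x+1) | log(x+0.1), ratio only | Log-link |
|---|---|---|---|---|---|---|
| 3% / 1% | 3.6 | 0.69 | 0.72 (44%) | 0.68 (53%) | 0.60 | 0.69 (46%) |
| 10% / 5% | 13.5 | 0.65 | 0.72 (41%) | 0.60 (55%) | 0.47 | 0.65 (51%) |
| 15% / 5% | 18 | 0.58 | 0.72 (41%) | 0.46 (82%) | 0.29 | 0.58 (68%) |
| 20% / 5% | 22.5 | 0.51 | 0.72 (40%) | 0.37 (95%) | 0.18 | 0.51 (81%) |

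Hand check of one rejection rate (15% / 5%, zeros dropped): the contrast is 2 ln 0.85 = −0.325. Positive responses per cell are 45 × 0.85 = 38.25 and 45 × 0.95 = 42.75. SE = 0.6 × √(2/38.25 + 2/42.75) = 0.189, so z = 1.72 and power is Φ(1.72 − 1.96), about 41%.

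**Does one method win?** No. With 10% zeros in every cell and amount 25% lower, dropping zeros rejects 86%, a two-part test 78%, log-link 72% and log(x+1) 43%, which reverses the order in the table.

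**Is any single method invalid under no effect?** With 10% zeros in every cell, dropping zeros rejects 5.0%, log(x+1) 4.3%, log-link 5.2%, zero against any 5.4% and two-part 4.9%.

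**The case for a change.** The strongest case for a change is that remedies chosen after unblinding can give different answers. At 15% and 5% zeros the estimate runs from 0.29 to 0.72 depending on the remedy. Units matter too. For spending with median $6 and log SD 0.8, zeros of 15% and 5% and no difference in amount, the overall ratio is (0.85/0.95)² = 0.80. There log(x+1) gives 0.67 in dollars (rejecting 34%) and 0.28 in cents (rejecting 56%). The plan already writes a contingency for quitters on cigarettes per day, and a sentence for demand would cost almost nothing.

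The arithmetic stands, and so does the point that the choice is better made before the data are seen. The rest is weaker. The wide spread needs zeros that are both common and unequal across cells, and nothing in the documents supports such rates. The 0.72 from dropping zeros is correct for amount among those with any demand, and it counts as biased only if overall demand is the target, which the plan does not specify. A request to name any one method would not remove the spread, because the acceptable methods themselves differ. The contingency for cigarettes per day protects the primary outcome, and a secondary measure does not need equal detail. Cost sensitivity for a person with no demand at any price stays undefined under every method, so the analyst can only count and report such cases.

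**Conclusion.** No change follows. This is missing operational detail for a secondary measure, of a kind that analysts have to settle in the ordinary course because log(0) cannot be computed. The plan does not prescribe the poorest option, and the harm appears only if that option is taken and zeros are frequent and uneven.

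If zeros are rare (1% to 3%, assumed), dropping them moves the ratio from 0.69 to 0.72 and rejection is 44%, against 46% with a log-link. The added constant still matters somewhat there, at 0.68 with 1 and 0.60 with 0.1. If zeros are common and uneven (15% and 5%, assumed), dropping them gives 0.72 against 0.58 for overall demand, and a reader of the report would need to know which quantity was estimated. Both statements rest on the assumed zero rates, median, log SD and 15% difference in amount. E-cigarette demand and cost sensitivity were not simulated. The cigarettes-per-day analysis, the preference-task choices and the sample size of 45 per group do not depend on the point.

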Because nicotine delivery and sensorimotor characteristics are a joint function of e-liquid and device characteristics, smokers may choose products that produce the optimal nicotine delivery and sensorimotor stimulation. Thus, we expect (hypothesize) an interaction between concentration and power, and this becomes our **core scientific premise**. A higher-powered device that can deliver greater nicotine per puff of aerosol is likely to be more reinforcing when it is paired with a low nicotine concentration because this combination produces the optimal level of nicotine delivery. Low nicotine concentrations paired with low power may not deliver enough nicotine or provide enough sensorimotor stimulation to be reinforcing, while high nicotine concentrations paired with high power may provide aversive levels of nicotine or an aversive throat hit. Consistent with this prediction, a small study of 20 e-cigarette users found that users of higher powered devices used lower e-liquid nicotine concentrations than users of lower-powered devices, but obtained higher levels of plasma nicotine. Furthermore, a recent survey of 436 current e-cigarette users found a strong negative relationship between the power of device settings and user's chosen e-liquid nicotine concentration ( $r = -0.44$ ). In one experimental lab study, smokers reported that a lower concentration was required to produce the optimal throat hit when using a higher power setting. However, we also know that e-cigarette users can compensate for changes in these characteristics by modifying their puffing behavior. When device power or nicotine concentration are lower, e-cigarette users have been shown to take longer puffs, more puffs, and ultimately consume more e-liquid. Thus, an alternative hypothesis is that these characteristics may be relatively unimportant, as long as users are able to modify their behavior in order to achieve the desired effect. The interactive effects of concentration and power remain unclear, and serve as the central focus of this application.

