### C8. Statistical Considerations:

Power analysis was completed for the primary outcome of percentage reduction in average cigarettes per day smoked in the last week of sampling, and based on data from [name] previous e-cigarette sampling trial during which participants received a low power (1st Gen) device with one of two nicotine concentrations (low or high). We hypothesize that the impact of nicotine concentration on CPD reduction would be similar here for the low power groups and that the effect would be reversed, but of similar size, in the high-power groups (Figure 3a). The hypothesized interaction is shown during the last week of sampling for simplicity in Figure 3b, specifically that for the low power setting, a higher concentration will produce a larger decrease in cigarettes per day than the low concentration, but for the high-power setting, a higher concentration will produce a smaller decrease in cigarettes per day than the low concentration. We use the methods described by Fleiss for estimating power for interaction effects. As he notes, the variance of an interaction effect is four times that of the corresponding main effect. Thus, even large effects require large sample sizes to yield adequate power. In this case, a sample size of 40 participants / group will provide 80% power to detect an interaction among the two factors with a 0.050 significance level, assuming that the common standard deviation is 38% reduction in CPD, as was the case in [name] trial. However, we inflate this sample size by 10%, accounting for attrition over time, and thus aim to **recruit 45 participants randomized per group (total N=180)**.

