For aims 1 and 2, we will assess the impact of concentration and power on each outcome across time using a generalized estimating equation that includes concentration, power, sampling week (time), and their interactions. Hypothesis 1 will focus on percentage reduction in CPD, Hypothesis 2 will focus on e-cigarette uptake (puffs per day), and Hypothesis 3 will focus on complementary measures of preference/demand, all of which are captured at Visit 4. Outcomes that are skewed (e.g., demand parameters, urinary cotinine) will be log transformed. It is possible that reductions in CPD will be bimodal in the last week of sampling, reflecting a subset of participants who may quit smoking during the trial. In this case, we would conduct a Chi-square test on the proportion of participants who reduce their smoking by at least 50%. Exploratory analyses on age will be conducted by adding age to the model. [name] (co-mentor) will be meeting with [name] monthly for training in these analyses, and will also be available to assist with the eventual power analysis for the R01 submission based on these data.

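### If last-week CPD reduction is bimodal, the plan falls back on a Chi-square of 50% responders that is not set up to test the concentration-by-power interaction

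*Combined protocol and SAP*

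**What the plan says.** The interaction is the scientific target throughout. Section A2 states: "we expect (hypothesize) an interaction between concentration and power, and this becomes our" core premise. Specific Aim 1 opens its first hypothesis with "There will be an interaction such that a higher (vs. lower) nicotine concentration will produce greater reductions in CPD and CO" at low device power, and predicts the opposite at high power. Section C8 repeats the second half: "for the high-power setting, a higher concentration will produce a smaller decrease in cigarettes per day than the low concentration". For sizing, the SAP assumes that "the effect would reversed, but of similar size, in the high-power groups", and claims that 40 per group "will provide 80% power to detect an interaction among the two factors with a 0.050 significance level".

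The main analysis matches this target. Outcomes under Aims 1 and 2 are analysed "using a generalized estimating equation that includes concentration, power, sampling week (time), and their interactions".

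The contingency for the primary outcome does not carry the target over. Section C8 and the SAP both warn: "It is possible that reductions in CPD will be bimodal in the last week of sampling", because some participants may quit. They then give one sentence: "In this case, we would conduct a Chi-square test on the proportion of participants who reduce their smoking by at least 50" per cent. Neither place names the groups compared, the table layout, the degrees of freedom or an interaction contrast. Neither gives a criterion for bimodality, or says whether the Chi-square replaces the GEE or accompanies it.

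**The concern.** A Chi-square on a proportion becomes a test of something only once the table is defined, and the layouts an analyst would ordinarily choose do not isolate an interaction. The sponsor itself foresees the scenario, and it concerns the outcome on which the trial was sized.

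Two errors become possible. A significant four-group result, or significance at one power level only, could be reported as support for Hypothesis 1 when only a main effect exists. Conversely, a true reversal could be missed by a test not aimed at it. If the Chi-square replaces the GEE, CPD may be left with no interaction test. If it accompanies the GEE, two results bear on one hypothesis with no stated order of precedence.

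**Working it through.** **The plan's own figure.** Inputs from the SAP: 40 per group, SD 38 points, alpha 0.05 (two-sided assumed), 80% power. The standard error of the difference in differences is 38 × √(4/40) = 12.02 points. Power of 80% then needs (1.96 + 0.84) × 12.02 ≈ 33.7 points, or about 16.8 points each way. The text gives no effect size to compare with this; the hypothesised pattern is in figures not reproduced in the copy reviewed. Attrition: 40/0.90 = 44.4, rounded up to 45 per group, 180 in total, as stated. The sizing therefore concerns a 1-df interaction contrast on the continuous outcome.

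**Worked table for the fallback.** Assumed: 40 per cell, with 4 (10%) or 10 (25%) responders. Cell order: low concentration/low power, high/low, low/high, high/high. Pearson statistics are without continuity correction.

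| Layout | Reversal (4, 10, 10, 4) | Concentration effect only (4, 10, 4, 10) | Power effect only (4, 4, 10, 10) |
|---|---|---|---|
| Four groups, 3 df | 6.23, p = 0.10 | 6.23, p = 0.10 | 6.23, p = 0.10 |
| By concentration, pooled over power | 14/80 vs 14/80, p = 1.00 | 8/80 vs 20/80, p = 0.013 | 14/80 vs 14/80, p = 1.00 |
| By power, pooled over concentration | 14/80 vs 14/80, p = 1.00 | 14/80 vs 14/80, p = 1.00 | 8/80 vs 20/80, p = 0.013 |
| Within each power level | 3.12, p = 0.077, opposite directions | 3.12, p = 0.077, same direction | 0 |
| Diagonal 2×2 | 20/80 vs 8/80, 6.23, p = 0.013 | 0 | 0 |
| Product term, risk difference | 6.49, p = 0.011 | 0 | 0 |
| Product term, logit | 5.87, p = 0.015 | 0 | 0 |

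The diagonal 2×2 sets the two cells hypothesised to reduce more against the other two.

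Formulas:
- Four groups: 160 × 0.075² / (0.175 × 0.825) = 6.23. The diagonal has the same value on 1 df.
- Within a power level: 80 × 0.075² / (0.175 × 0.825) = 3.12.
- Risk-difference interaction: (0.15 + 0.15)² / [2(0.10 × 0.90)/40 + 2(0.25 × 0.75)/40] = 0.09/0.013875 = 6.49.
- Logit interaction: 2.197² / [2(1/4 + 1/36) + 2(1/10 + 1/30)] = 2.197²/0.822 = 5.87.

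With 6 or 14 responders per cell, the four-group statistic is 160 × 0.10² / (0.25 × 0.75) = 8.53, p = 0.036, for the reversal and for either main effect alike. This follows from the test itself: permuting the cell labels leaves the four-group statistic unchanged.

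**Rejection rates in a bimodal simulation.** Assumed: 40 per cell; 10% or 25% quitters at 100% reduction; non-quitter mean reduction 0–30 and SD 20–35; 20,000 trials per scenario.

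| Test | Reversal | Main effect only |
|---|---|---|
| Four-group | 18–52% | 19–52% (power) |
| Pooled over either factor | 4–5% | – |
| By power level: exactly one significant | 28–49% | 29–49% (concentration) |
| Diagonal 2×2 | 27–70% | 4–5% |
| Product term, risk difference | 29–72% | 5–6% |
| Product term, logit | 27–67% | 3–5% |
| Interaction in means | 37–63% | 5% |

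**Closer to the plan's implied effect.** Responder rates were also derived from a normal model (not bimodal) with SD 38, a 16.8-point effect each way and mean reduction 20–50% in the lower cells. At 40 per cell, power under the reversal is 39–43% for the four-group test, 54–61% for the interaction contrast and 4–5% for pooled tables.

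**The case against.** The text never says the Chi-square is run instead of the GEE. The GEE sentence covers every outcome under the two aims and nothing withdraws it, so the Chi-square may be only a supplementary responder check. Carbon monoxide keeps its interaction model on either reading. That stands. It narrows the harm, but leaves the responder test undefined and the two results unranked.

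Tests by power level are also not uninformative. Both significant in opposite directions is the pattern the hypothesis describes. In the simulation this occurred in 3–18% of trials under the reversal, and in at most 0.2% under a main effect at the two extreme settings checked. So that joint result is specific, but far too rare to serve as the test.

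A diagonal Chi-square would perform almost as well as a product term. This is correct, and a Chi-square on the product term would also serve. The plan names neither.

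The simulated bimodal effects are smaller than the roughly 16.8 points implied by the sizing, so their absolute power figures should not be read as the trial's. That also stands. The invariance of the four-group test and the cancellation on pooling are unaffected.

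Finally, this is a contingency: if the outcome is not bimodal, nothing changes.

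**Conclusion.** The concern holds and should be fixed. For a scenario the sponsor foresees on its primary outcome, the plan states no test of the interaction that the trial is designed to detect. The four-group layout gives identical statistics for a reversal and a main effect. Pooling over either factor has no power against an equal reversal beyond the nominal error rate.

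These two results are structural. The p values and rejection rates rest on assumed responder and quit rates. Over assumed quit rates from 5% vs 15% up to 10% vs 30% and 20% vs 40%, four-group rejection moves from 11–37% up to 31–76%, always within about 2 points of the main-effect rate. The missing bimodality criterion and order of precedence are secondary; the missing interaction test is the substance.

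**What to change.** In the SAP and in C8, replace the Chi-square with a logistic, binomial-GEE or risk-difference model for at least 50% reduction, containing concentration, power and their product. Name the scale and make the product term the test. State in advance that the GEE on percentage CPD reduction is reported regardless, and which of the two governs Hypothesis 1, so that the choice does not depend on an undefined look at the distribution.

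The cost is one or two sentences in each place and one extra model, with no new data and no change to design or sample size.

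One caveat should be written down: the stated 80% power belongs to the continuous outcome and does not carry over to the responder interaction. Neither analysis always has more power. In the simulated cases the risk-difference responder test had more when non-quitters did not reduce on average (56–72% against 48–63% for means), and less when they reduced by 30% on average (29–43% against 37–55%). The order of precedence is therefore the sponsor's choice, provided it is fixed beforehand.
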